7.4 Randomization

If it is determined that the participant meets all eligibility criteria, then randomization to one of the four treatment arms will be implemented. Participants will be randomized in equal proportions to one of the four treatment arms, using a randomized block design stratified by clinical site. At the time of randomization, the participant will be provided with two (2) tamper evident bottles of study medications and thorough instructions on how to take each of them. Details of the participant instructions will be provided in the Manual of Procedures (MOP).

7.5 Week Three (3) Telephone Contact

The Participant contact at week number three (3) post randomization is completed via telephone. During this contact, participants will be instructed to complete, and mail back to the clinical center, self administered forms, as well as answer questions regarding follow-up contacts and adverse events.

Self Administered Forms:

1. NIH-CPSI
2. MOS-SF12
3. Follow-Up Symptoms

Telephone Contact:

1. Follow-Up Contact
2. Adverse Events/Serious Adverse Events

7.6 Week Six (6) Clinic Visit

The Participant visit at week number six (6) will be a clinic visit. At this time, participants complete the following indices or forms as well as undergo the following procedures.

Clinic Visit Indices:

1. NIH-CPSI
2. MOS-SF12
3. Follow-Up Symptoms
4. Follow-Up Contact
5. Adverse Events/Serious Adverse Events
6. Voiding Log
7. Medication Diary
8. Concomitant Medications
9. Treatment Stop Form

Clinic Laboratory Procedures and Physical Exam:

1. Four Glass Microscopy and Culture Test
2. Post Void Residual
3. Physical Examination
4. Semen Sample (collected only if participant has localized uropathogens at baseline. Participant will be scheduled 2-3 days following clinic visit for semen sample collection).

7.6.1 Study Treatment Completion

Each participant will be required at week number six (6) to complete a Treatment Stop Point form. Participants will report any and all reasons for stopping treatment medications prior to week six (6).

7.7 Week Nine (9) and Twelve (12) Telephone Contact

The Participant contacts at week number nine (9) and week number twelve (12) post randomization are completed via telephone. During these contacts, participants complete the following indices or forms:

1. NIH-CPSI
2. MOS-SF12
3. Follow-Up Symptoms
4. Follow-Up Contact
5. Adverse Events/Serious Adverse Events
6. Study Stop Point (*Week Twelve (12) only*)

7.7.1 Rescue Medications

At anytime during the post treatment phase of the trial, participants may use a “rescue medication” for symptoms related to their chronic prostatitis. Participants will receive a packet of forms at their last clinic visit (week 6) with instructions on reporting rescue medication. Participants are required to inform the Research Coordinator when they take any form of a rescue medication.

8 ADVERSE EVENTS AND PARTICIPANT WITHDRAWAL

The Investigator(s) will be required to provide appropriate information concerning any findings that suggest significant hazards, contraindications, adverse events, or precautions pertinent to the safety of the drug under investigation. Details of adverse events reporting are described below.

8.1 Definitions of Adverse Events (AEs)

An Adverse Event is **ANY** unfavorable and unintended sign, symptom, or disease temporarily associated with the use of a medicinal product, whether or not considered related to the medicinal product.

All AEs will be reported to the study investigator and recorded on a case report form.

8.2 Definition of Serious Adverse Events (SAEs)

A serious adverse event is defined as any untoward (unwanted) medical occurrence that at **ANY** dose

- Results in death
- Is life-threatening
- Results in a persistent of significant disability/incapacity
- Results in in-patient hospitalization or prolongation of existing hospitalization
- Results in a congenital anomaly/birth defect

Important medical events that may not result in death, be life threatening, or require hospitalization may be considered a serious adverse drug experience when, based upon medical judgment, they may jeopardize the patient or participant and may require medical or surgical intervention to prevent one of the outcomes listed in this definition. Examples of such medical events include allergic bronchospasm requiring intensive treatment in an emergency room or at home, blood dyscrasias or convulsions that do not result in inpatient hospitalization, or development of drug dependency or drug abuse.

8.3 Reporting Obligations for SAEs and IND Safety Reports

The Clinical Site is responsible for reporting SAEs to the DCC within 24 hours of first knowledge of the event via telephone, followed by a facsimile, (which includes both the corresponding **AE Case Report Form** and the **MedWatch** Form). In addition, the site must promptly report all SAEs to their **IRB via written/dated notification** in accordance to the IRB's reporting requirements. Copies of all such correspondence must be maintained in the clinical site's main study binder. All SAEs must be followed with appropriate medical management until resolved.

Upon Notification from the clinical site, the DCC will notify the sponsor (NIH/NIDDK) of SAEs within one (1) working day. Should any SAEs fall into the category of IND Safety Reports (serious, unexpected, and possibly related to drug), the DCC, as designated by the NIH/NIDDK, will report the event to the FDA and all investigational sites in accordance to the process and timelines specified in the FDA regulations. DCC will serve as the sponsor's designee by disseminating the IND safety reports to all clinical sites and promptly notifying the Licensed Product Holders.

8.4 Potential Adverse Events

8.4.1 *Ciprofloxacin Hydrochloride (CIPRO®)*

During clinical investigation with the tablet, the most frequently reported events, drug related or not, were nausea (5.2%), vomiting (2.0%), abdominal pain/discomfort (1.7%), and rash (1.1%). Most of the adverse events were described as only mild or moderate in severity, abated soon after the drug was discontinued and required no treatment. In randomized, double-blind controlled clinical trials comparing ciprofloxacin tablets (500mg BID) to cefluroxime axetil (250

mg-500 mg BID) and to clarithromycin (500 mg BID) in participants with respiratory tract infections, ciprofloxacin demonstrated a CNS adverse event profile comparable to the control drugs.

In several instances nausea, vomiting, tremor, irritability, or palpitation were judged by the investigator to be related to elevated serum levels of theophylline possibly as a result of the drug interaction with ciprofloxacin. Serious and fatal reactions have been reported in participants receiving concurrent administration of ciprofloxacin and theophylline.

Post-Marketing Adverse Events: Additional adverse events, regardless of the relationship to the drug, reported from worldwide marketing experience with quinolones, including ciprofloxacin, are:

- Change in serum phenytoin
- Postural hypotension, vasculitis
- Agitation, confusion, delirium, dysphasia, myoclonus, nystagmus, toxic psychosis
- Constipation, dyspepsia, flatulence, hepatic necrosis, jaundice, pancreatitis, pseudomembranous colitis
- Aganulocytosis, hemolytic anemia, methemoglobinemia, prolongation of prothrombin time
- Elevation of serum triglycerides, cholesterol, blood glucose, serum potassium
- Myalgia, possible exacerbation of myasthenia gravis, tendinitis/tendon rupture
- Albuminuria, candiduria, renal calculi, vaginal candidiasis
- Anaphylactic reactions, erythema multiforme/Stevens-Johnston syndrome, exfoliative dermatitis, toxic epidermal necrolysis
- Anosmia, taste loss

Adverse Laboratory changes: Changes in laboratory parameters listed as adverse events without regard to drug relationship are listed below:

- Elevated ALT(SGPT), AST(SGOT), alkaline phosphate, LDH, serum bilirubin
- Eosinophilia, leukopenia, decreased blood platelets, elevated blood platelets, pancytopenia
- Elevations of serum creatinine, BUN, crystalluria, cylindruria, hematuria have been reported
- Other changes in <0.1%: elevation of serum gamma-glutamyl transferase, elevation of serum amylase, reduction in blood glucose, elevated uric acid, decrease in hemoglobin, anemia, bleeding diathesis, increase in blood monocytes, leukocytosis

Placebo

Inactive agent—Adverse events not expected.

8.4.2 Tamsulosin Hydrochloride (FLOMAX®)

Adverse events reported in the U.S. and European placebo-controlled clinical trials included: headache in 19%, infection in 9.0%, back pain in 7.0%, chest pain in 4.0%, asthenia in 7.8%, dizziness in 14.9%, somnolence in 3.0%, insomnia in 2.4%, decreased libido in 1.0%, rhinitis in

13.1%, pharyngitis in 5.8%, Increased cough in 3.4%, sinusitis in 2.2%, diarrhea in 6.2%, nausea in 2.6%, tooth disorder in 1.2%, abnormal ejaculation in 8.4% and amblyopia in 0.2%.

In two U.S. studies, symptomatic postural hypotension was reported by 0.2% of participants in the 0.4mg group, 0.4% of participants in the 0.8 mg group and by no participants in the placebo group. Syncope (0.2-0.4%), dizziness (15%), and vertigo (0.6%) were reported on 0.4 mg group and 0.4%, 17%, 1% on 0.8 mg, respectively.

Post-Marketing Experience: Allergic type reactions such as skin rash, pruritus, angioedema of tongue, lips and face and urticaria have been reported with positive rechallenge in some cases. Priapism has been reported rarely. Infrequent reports of palpitations, contipation and vomiting. Latest dated Package Insert (November, 1999).

Placebo

Inactive agent—Adverse events not expected.

8.5 Unmasking of Treatment

At the end of Baseline Screening Visit #2, participants will be randomized following a randomization schedule generated by the DCC prior to study initiation. Neither the Investigator nor the investigational site personnel will know the treatment group to which any participant is randomized. Unmasking of treatment assignment is anticipated to be an extremely uncommon occurrence and is strongly discouraged. If there is a serious adverse event, which is thought by the clinical site staff to be possibly or probably related to the coded medication, the clinical site staff, when necessary for the safety of the participant, may be permitted to request unmasking of treatment group assignment. Approval to unmask will be granted by the study's medical monitor in collaboration with the clinical site's Investigator.

The clinical site staff should contact the On Site Investigator, who would promptly page the medical monitor. If decided that unmasking is appropriate, the medical monitor should immediately contact the University of Pennsylvania Investigational Drug Service (IDS) with a request to unmask the treatment group assignment. The IDS Pharmacist will report the treatment arm to the On Site PI (or designee). The clinical site staff must report the unmasking to the DCC via within one (1) working day, to be followed by submission of a detailed report to the DCC within three (3) working days of the unmasking event. The clinical site must also promptly notify their IRB of the unmasking occurrence in accordance to reporting requirements.

In accordance to the ICH *Guideline for Industry Clinical Safety Data Management's* section on expedited reporting: "Although it is advantageous to retain the blind for all patients prior to final study analysis, when a serious adverse event is judged reportable on an expedited basis, it is recommended that the blind be broken only for that specific patient by the sponsor even if the investigator has not broken the blind. It is also recommended that, when possible and appropriate, the blind be maintained for those persons, such as biometrics personnel, responsible for analysis and interpretation of results at the study's conclusion." For the purposes of this protocol, if dissemination of this unmasking information from the Sponsor to the Licensed Product Holders is requested, a collaborative discussion/process is appropriate.

8.6 Participant Withdrawal

It is expected that up to 10% of participants may drop out of the trial due to side effects or lack of efficacy prior to the six (6) week endpoint. However, all attempts will be made to get complete data on all participants, including those who cease treatment prior to six (6) weeks, in order to conduct the primary intent-to-treat analysis. It is expected that a maximum of 15% of participants will withdraw completely from treatment AND follow-up prior to six (6) weeks.

Under certain circumstances, a study participant may have his treatment terminated prior to the six (6) week clinic visit. These circumstances include: unacceptable concomitant medications/treatments, unacceptable adverse events as determined by the Principal Investigator (PI), participant dissatisfaction with treatment, or participant disinterest in continued study participation. In addition, any participant who acquires a serious or life-threatening medical condition while participating in the study may have the study treatment terminated early at the discretion of the PI. A participant may also undergo early study termination because of a change of residence outside the driving distance of the CPCRn network.

9 ADMINISTRATIVE RESPONSIBILITIES

9.1 Institutional Review Board

It is the responsibility of the Principal and Co-Investigator(s) at each site to provide the appropriate Institutional Review Board (IRB) with all pertinent material, including a copy of the informed consent. Approval of the protocol and the informed consent form must be obtained and forwarded to the sponsor prior to screening or enrolling any subjects.

The Investigator also maintains the responsibility of initiating protocol re-approval, notification of protocol and/or consent form changes, notification of adverse reactions, and termination of the study according to the appropriate IRB requirements. A sample consent form is included in **Appendix B**.

9.2 Laboratory Accreditation

The Principal and Co-Investigator(s) must maintain documentation of adequate licensure or accreditation for all clinical laboratory facilities used for study sample analysis. In addition, the clinical laboratory's normal values for test results must be forwarded to the DCC prior to study initiation and annually thereafter. This documentation should cover the entire period the protocol is active.

9.3 Sponsor Monitoring/On-site Monitoring

The DCC has developed written standard operating procedures (SOPs) to ensure that all aspects of the randomized clinical trial are conducted in a standard and uniform manner. These procedures will be organized into a Manual of Procedures (MOP), which will comply with the protocol, GCP and applicable regulatory requirements. All study associated personnel will be trained in study conduct and procedures prior to the start of the trial. A data and safety monitoring plan and data-monitoring schedule will be developed to assess protocol adherence. This plan will be presented to the External Advisory Committee for approval for implementation.

9.4 Compliance with Agencies

The sponsor will ensure that this study is performed in compliance with applicable regulations associated with the Food and Drug Administration (FDA), the International Conference on Harmonization (ICH), (29) and the Declaration of Helsinki. The sponsors will also keep a 1572 (Statement of Investigator), and current CVs of all Principal Investigators and Research Coordinators on file.

9.5 Record Retention

The DCC must maintain all trial records for a period in accordance with their internal Standard Operating Procedures (SOP) and applicable regulations.

9.6 Direct Access to Source Documents

Investigators will maintain, on-site, in an orderly fashion, for a period of no less than seven (7) years, and make available to the sponsor or the sponsor's representative, the following documents: the signed study protocol, amendments, informed consent documents, investigator brochure, approval letters from the IRB, drug accountability forms, CRFs, all primary source documentation, and all letters of correspondence.

9.7 Data Management and Quality Assurance

The Data Coordinating Center (DCC) will coordinate all study activities pertaining to:

1. Design, development, production, testing and distribution of case report forms (CRFs) over the internet to the client workstations at each clinical center;
2. Collection, entry, verification, validation and query resolution of data; and
3. Quality Assurance monitoring and reporting.

Data management issues, especially those concerning data quality and integrity in multi-center trials, as discussed extensively in Meinert (30) DeMets (31) Neaton (32) Bailey (33), and McFadden (34), will be addressed within the Manual of Procedures (MOP) and emphasized during the Research Coordinator (RC) training prior to protocol initiation.

The DCC will develop and maintain a computerized Data Management System (DMS) for this Protocol that will be deployed over the WORLD WIDE WEB using standard Web Browser tools within each of the Clinical Centers. Case report forms (CRFs) will be available to be printed locally at the clinical centers from Portable Document Files (PDF). Originals of these forms will be retained by the clinical centers. Double data entry will be performed at the Clinical Centers, utilizing the DMS tools available on the clients' workstations. The DCC will deploy a WORLD WIDE WEB based data management system for the implementation of the randomized clinical trial (RCT#1). A distributed rather than centralized DMS will be utilized for data submission. To achieve distribution of the DMS, a Web Browser (such as Netscape) must be available locally and, clinical site personnel will access the study database (DMS) via the WORLD WIDE WEB by connecting to the Web Server that resides at the DCC. The DCC Web Server will in turn connect with the DCC Database Server (this is a standard three tiered architecture configuration), which will provide secure access to the applications, and databases, which comprise the DMS.

There will be a manual back-up system for implementing randomization of participants in the event the DMS system is not functional at the time that randomization is required.

Validation checks will be performed at the centralized database to verify data accuracy and identify missing, unclear, illogical, or problematic responses. Queries will be generated to resolve discrepancies. Confidentiality will be strictly adhered to by assigning a unique participant identifier that will not identify the subject by name. The Manual of Procedures will define these processes in detail.

10 STATISTICAL CONSIDERATIONS

The proposed study design is a four-arm, double blind, RCT utilizing a 2×2 factorial design to evaluate the effect of oral ciprofloxacin (CIPRO®) and/or oral tamsulosin hydrochloride (FLOMAX®) in CP. An inactive placebo will be used for both ciprofloxacin (CIPRO®) and tamsulosin hydrochloride (FLOMAX®). The four treatment arms will be 1) placebo plus placebo, 2) ciprofloxacin (CIPRO®) plus placebo, 3) tamsulosin hydrochloride (FLOMAX®) plus placebo, 4) ciprofloxacin (CIPRO®) plus tamsulosin hydrochloride (FLOMAX®). A total of 184 participants will be enrolled. Details of the design considerations and statistical analysis, including sample size and power considerations, are described in the following sections. Additional details will be provided in the study Data Analysis and Monitoring Plan (DAMP), provided prior to study initiation.

10.1 Randomization and Stratification

To ensure balance across treatment groups within each clinical center, a stratified randomization approach will be used. Within each of the ten (10) clinical sites, subjects will be randomly allocated in equal proportions to the four treatment arms using a permuted block randomization procedure. In order to maintain blinding, each subject will be given a unique identifier number. The treatment code will be known only to the University of Pennsylvania Investigational Drug Service and the Data Coordinating Center Quality Assurance Manager until the completion of treatment and data collection on all participants.

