10.3.2 Statistical Analyses

In addition to the analyses described subsequently, descriptive statistics will be used during the course of the project as part of data management procedures for monitoring data quality. A brief overview of some of the statistical methods that may be used at the time of analysis, both for descriptive purposes and in more comprehensive analysis of the primary research questions, is summarized in the following sections. It is recognized that these methods may be revised, and additional ones considered, as the details of the specific analyses are developed. Details of the statistical analysis will be outlined in the Data Analysis and Monitoring Plan (DAMP).

Descriptive Analyses

Standard descriptive statistics will be used to describe baseline characteristics and follow-up measures, both overall and within each treatment group. Examination of baseline characteristics will include estimates of the distribution of age, race, and other demographic characteristics, baseline severity based upon pain/discomfort, urgency and frequency, and clinical center. These factors will be examined, both separately for each center, and combined across centers. Summary statistics such as means, medians, and ranges will be produced for all measured variables. Frequencies will be computed for all categorical and ordinal variables. Graphical methods including stem-and-leaf diagrams and boxplots will be used to examine distributions, identify potential influential points, and guide in the choice of transformations if warranted. The balance of baseline measures across the treatment groups will be compared using appropriate 2-sample and k-sample tests including analysis of variance (ANOVA), Wilcoxon and Kruskal-Wallis tests, and Fisher's exact tests.

Analysis of Primary Outcome

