10.3.3 Final Analysis

The final analysis of the data will take place after the completion of accrual, follow-up, and data collection and validation on all subjects. Details of the plans for final analysis will be outlined in the Data Analysis and Monitoring Plan (DAMP).

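### Section 10.1 lets the treatment code open when data collection ends, before the validation and query resolution that Section 10.3.3 requires ahead of the final analysis

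*Protocol*

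**What the plan says.** Four parts of the protocol bear on this.

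- **Who holds the code and for how long (10.1).** "The treatment code will be known only to the University of Pennsylvania Investigational Drug Service and the Data Coordinating Center Quality Assurance Manager". The restriction runs "until the completion of treatment and data collection on all participants". Validation, query resolution and database lock are not part of the condition.
- **When the final analysis starts (10.3.3).** It takes place "after the completion of accrual, follow-up, and data collection and validation on all subjects".
- **What happens to data after collection (9.7).** The coordinating centre's tasks include "Collection, entry, verification, validation and query resolution of data". On content: "Validation checks will be performed at the centralized database to verify data accuracy and identify missing, unclear, illogical, or problematic responses", followed by "Queries will be generated to resolve discrepancies".
- **How firm the methods are (10.3.2).** The section introduces its content as an overview of "some of the statistical methods that may be used at the time of analysis" and adds: "It is recognized that these methods may be revised, and additional ones considered, as the details of the specific analyses are developed".

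Two further statements limit the concern. The opening of Section 10 promises the DAMP before the study starts. Section 10.3.2, under the primary outcome, commits to a linear regression (two-way analysis of variance) with a random centre effect.

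**The concern.** A masking rule should hold until nobody's decision can still alter the data set or the primary analysis. Here it stops at the end of collection. Validation looks for missing, unclear or illogical answers and raises queries, so a stored value can change as a result.

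If the code is open at that stage, a decision on whether to raise a query, how to settle an ambiguous answer, or whether to treat an item as missing could be made by someone who knows the arm. The primary endpoint is a self-reported total over several items, so ambiguous or missing items are a realistic source of queries. Even if nobody acts on the knowledge, a reader of the results could not tell from the protocol that such decisions were made masked.

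The lesser issue is that no sentence in the protocol makes unmasking the point after which a change to the primary analysis has to be declared.

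**Working it through.** No stated figure is in question, so the check is a comparison of the text.

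**Step 1: are collection and validation the same step?** Three milestones matter: C, the end of data collection; V, the end of validation and query resolution; F, the start of the final analysis.

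| Section | Condition | Milestones named |
|---|---|---|
| 10.1 | code restricted until | C (and end of treatment) |
| 9.7 | coordinating centre tasks | collection listed apart from validation and query resolution |
| 10.3.3 | final analysis after | C and V (and end of accrual and follow-up) |

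Sections 9.7 and 10.3.3 both name collection and validation separately. Taking the terms as the protocol uses them, V is distinct from C. It cannot come before C for the last records collected, since a record must exist before it can be checked.

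**Step 2: what protects the interval from C to V?** Section 10.1 no longer applies after C. Section 10.3.3 holds back the analysis until V, but it does not mention the code. Section 9.7 describes the checks and queries without any masking condition. The protocol contains no database-lock requirement tied to the code. The interval is therefore unprotected by the text.

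**Step 3: which data are exposed?** Section 10.1 refers to data collection on all participants, and follow-up runs to week 12. The primary endpoint is measured at week 6. For the last man enrolled, the code thus stays closed for about 12 − 6 = 6 weeks after his primary assessment. Many primary-endpoint queries could be settled masked in that time, but nothing requires it. The last-collected week-12 data, used for durability of response and time to rescue medication, have no such margin.

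**Step 4: is the analysis method also open at that point?** The revision sentence in 10.3.2 has no end date. However, that sentence speaks of details still being developed, and the same paragraph sends those details to the DAMP, which is due before the study starts. The primary model is stated as a commitment. What remains is that nothing in the protocol says a later revision must precede unmasking or be labelled if it does not.

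**The case against.** The strongest case on the other side has five parts.

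- **The wording permits early release; it does not order it.** True. But a masking rule works by prohibiting, and this one stops prohibiting before validation is complete.
- **Cleaning is largely concurrent.** Sections 10.3.1 and 10.3.2 describe data-quality monitoring during the trial. Section 9.7 has double entry at the centres, which keep the original forms, so answers to queries are anchored to source. This stands, and it reduces the likely number of late, arm-aware decisions. It does not reduce them to none.
- **The DAMP or the Manual of Procedures may require a lock.** Neither is shown, so this is possible. It would then differ from the release point that the protocol itself states, and 10.1 should still be aligned.
- **Section 8.5 quotes guidance that analysts stay masked where possible.** That guidance is cited for unmasking a single patient during the trial. It sets no release point at the end.
- **Methods are effectively fixed.** This largely stands. A reader might infer from 10.3.2 that the primary model is open to choice once arms are known, including removal of outlying points. The document does not support that. The model is named, 10.3 calls for all available data on all randomized men, the diagnostics are there to examine points with no provision for excluding them, the remark on transformations sits under descriptive analyses, and covariate-adjusted models are labelled secondary.

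**Conclusion.** The point holds as a mismatch between two stated rules: the code may open at the end of collection, while the protocol's own final analysis waits for validation. It rests on reading collection and validation as distinct steps, as 9.7 and 10.3.3 do. If 10.1 meant collection to include validation, the amendment simply says so. The gap on method revision is secondary, for the reasons given above.

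Two stronger readings should not be drawn.

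- **An inflated type I error.** A reader might want to attach a figure by simulating a choice of the smallest p-value among several analyses. Such a figure would need analyses that the protocol does not offer as primary and a covariate correlation that it does not give. It would also not isolate the interval between collection and validation, because the same selection could happen after lock if methods were not fixed. No error-rate figure is claimed.
- **A conflict in who holds the code.** A reader might infer that the Quality Assurance Manager both knows the arms and resolves queries. Section 9.7 gives those tasks to the coordinating centre as an organization. The inference rests on a job title, and no change of custodian is asked for.

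The size is therefore modest and not quantifiable from the document. It is worth correcting because the correction is free.

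**What to change.** Make two wording changes.

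1. In Section 10.1, replace the end point of the restriction with: *until all data have been validated, queries resolved and the database locked*. This brings it into line with 10.3.3. Individual unmasking for safety under 8.5 is unaffected.
2. In Section 10.3.2, after the sentence on revision, add: *any change to the primary analysis made after unmasking will be reported as post hoc*.

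If the DAMP or the Manual of Procedures already has a lock procedure, 10.1 can refer to it.

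The cost is two sentences. There is no effect on patients, visits, sample size or power. The only operational consequence is that general release of the code waits for validation, which the final analysis must wait for anyway.
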